9.0 TREATMENT/INTERVENTION PLAN

9.1. Study Treatment

The investigational agents to be used in this study are copanlisib and ibrutinib. Copanlisib is given intravenously on days 1, 8, and 15 of 28 day cycles. Ibrutinib is given orally every day on 28 days cycles. The maximum duration of treatment is 36 cycles not exceeding 36 months. Dose changes or interruptions are allowed per below guidelines and must be recorded appropriately.

Study personnel will maintain a log of all drugs supplied to the patient. Drug supplies for each patient will be inventoried and accounted for. Subjects will be given diary cards to complete for the ibrutinib taken at home. Subjects must bring the diary cards to the site on every visit so study site personnel can verify compliance.

9.1.1 Copanlisib administration:

Copanlisib is supplied as lyophilized preparation in a 6-mL injection vial. The total amount of copanlisib, BAY 80-6946, per vial is 60 mg. The solution for IV infusion is obtained after reconstitution of the lyophilisate with 0.9% sodium chloride solution. Please refer to the Pharmacy Instructions for detailed instructions for the reconstitution of the lyophilisate and for further dilution of the reconstituted solution. Study drug is administered in a normal saline solution, intravenously, over 1 h (or per MSK protocol). No intravenous glucose preparations should be administered on the days of infusion. Dosing is weekly for the first 3 weeks of a 28-day cycle (on Days 1, 8, and 15), followed by a 1-week break (i.e., no infusion on Day 22). Patients will be on 30 mg, 45 mg or 60 mg depending on their dose level.

Laboratory blood tests on day 1 of copanlisib treatment must follow the below criteria:

Table 9-1: Laboratory test criteria for Day 1 dose of subsequent cycles

Laboratory Test	Criteria for Day 1 dose (Cycle 2 and higher)
Glucose	< 160 mg/dL (fasting) or < 200 mg/dL (non-fasting)
Hemoglobin	$\geq 8 \text{ g/dL}$ ^a
ANC	$\geq 1 \times 10^9$
Platelets	$\geq 75 \times 10^9$ ^b

ANC = Absolute neutrophil count;

a: If hemoglobin is < 8 g/dL but $\geq 6 \text{ g/dL}$ on the day of planned study drug administration it is permissible to give the study drug dose as scheduled and transfuse within 48 hours after the dose, if the patient is hemodynamically stable and in opinion of investigator benefits outweigh risks. Rationale and treatment should be recorded in source document and eCRF.

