9.7. Dose Continuation, Modification and Interruption

Subjects will be evaluated for AEs at each visit with the NCI CTCAE v5.0 used as a guide for the grading of severity. Prior to completion of cycle 1 in both dose escalation or dose expansion phase, treatment with either ibrutinib, copanlisib or both may be interrupted for \leq 7 days for any reason and then resumed at the same dose. If patients take less than 2 infusions of copanlisib or less than 14 days of ibrutinib during the intended dose of cycle 1, they will be excluded from the DLT analysis and replaced. However if a patient takes less than 14 days of the intended dose of cycle 1 due to a DLT, they will be included in the DLT analysis and not replaced. After completion of cycle 1, study drugs (either ibrutinib, copanlisib) may be interrupted for \leq 28 days for any reason and then resumed at same or reduced dose. The investigator may remove any patient from study for any toxicity if the investigator believes it is in the best interest of the patient to discontinue study treatment.

Intrapatient dose reduction will not be allowed during cycle 1 unless a DLT has occurred and been counted. This is in order to accurately determine the safe and tolerable dose of copanlisib when used in combination with ibrutinib. Dose reductions may be made to ibrutinib and/or copanlisib during cycles 2 and beyond. If a toxicity can be ascribed to a specific study drug, then that drug may be dose modified while the non-offending drug may be maintained. Whether to dose modify ibrutinib or copanlisib is at the discretion of the treating physician.

If the patient experiences unacceptable toxicity that fails to resolve after a maximum dose delay of 28 consecutive days, then the patient should be discontinued from the study treatments. In cases of treatment delays from reactivation of CMV, treatment delays can be extended for up to 2 months. In exceptional situations, if the patient is clearly benefiting from the study treatment (i.e. stable disease or better) and in the opinion of the investigator no safety concerns are present, the patient may remain on the study treatment. Patients who discontinue from study for a study related adverse event or an abnormal laboratory value must be followed as described in Section 10.

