Each patient is allowed a maximum of two dose reduction of each study drug. Dose reduction of copanlisib or ibrutinib indicates treatment at the next lower dose of copanlisib or ibrutinib based on Table 9-6. If after treatment interruption, resolution of toxicity, and treatment resumption at same dose, the subject presents with the same toxicity at the same severity, then the next treatment re-

initiation must resume at the next lower dose level irrespective of duration. A patient must discontinue therapy if after therapy is resumed at a lower dose, the same toxicity recurs with the same or worse severity. Copanlisib and ibrutinib dose modification guidelines for specific toxicities are outlined in Table 9-7.

Table 9-6. Intrapatient dose reduction*

Drug	Maximum Dose Levels	Reduction Dose Level 1	Reduction Dose Level 2
Copanlisib	60 mg	45 mg	30 mg
Ibrutinib	560 mg daily	420 mg daily	280 mg daily

*Dose reduction starts from the treating dose.

Dose escalation is allowed after the DLT period for ibrutinib to the FDA approved dose levels of 560 mg. However, patients will only be allowed to escalate to this dose once the DLT evaluation period for Dose Level 1 has passed and the dose will not exceed what has been deemed the MTD in other patients. There will be no intrapatient dose escalation of copanlisib. Once a dose reduction for copanlisib of a patient has occurred, the dose level may not be re-escalated during subsequent treatment cycles.

The sections below describe dose reduction steps for patients enrolled in the expansion phase of the study. For patients in the dose expansion phase, the dose must be held per these guidelines and these dose reduction steps can be followed after cycle 1 and per discussion with the PI. Inability to meet treatment criteria will result in holding the dose. If patients have been dose reduced to dose level -1 and continue to meet dose modification criteria to reduce the dose, they will be removed from study treatment.

Table 9-7. Dose modification guidelines

Toxicity Category	Severity (CTCAE 5.0 Grade)	Dose Modifications for ibrutinib	Dose Modifications for copanlisib
HEMATOLOGIC			

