Anemia	Grade ≥ 3 (Hgb <8 g/dL)	Investigator discretion for ibrutinib dosing	
Delay copanlisib infusion until Hgb resolves to \leq grade 3
 
Dose reduction by 1 dose level lower at the investigator's discretion. If more dose reductions are required than allowed per protocol, discontinue copanlisib permanently. The lowest dose level is 30 mg.

May dose modify/hold either ibrutinib, copanlisib or both as clinically indicated			
Neutropenia	Grade 1 (ANC < LLN - $1.5 \times 10^9/L$) Grade 2 (ANC < $1.5 - 1.0 \times 10^9/L$)	Maintain ibrutinib dose	Maintain copanlisib dose
	Grade ≥ 3 (ANC < $1.0 \times 10^9/L$)	
Delay ibrutinib dose until resolves to \leq Grade 1, then: If resolved \leq 7 days, then maintain dose level If resolved $>$ 7 days, then reduce 1 dose level
 
Growth factor support is allowed after cycle 1.
	
Delay copanlisib infusion until ANC resolves to $<$ grade 3
 
Dose reduction by 1 dose level lower at the investigator's discretion. If more dose reductions are required than allowed per protocol, discontinue copanlisib permanently. The lowest dose level is 30 mg.
 
Growth factor support is allowed after cycle 1.

	Febrile neutropenia ($ANC < 1.0 \times 10^9/L$, with a single temperature of $\geq 38.3^\circ C$ or a sustained temperature of $\geq 38^\circ C$ for more than one hour)	
Delay ibrutinib dose until resolves to \leq Grade 1, then reduce 1 dose level
 
Growth factor support is allowed after cycle 1.
	
Delay copanlisib until febrile neutropenia resolves
 
Dose reduction by 1 dose level lower at the investigator's discretion. If more dose reductions are required than allowed per protocol, discontinue copanlisib permanently. The lowest dose level is 30 mg.
 
Growth factor support is allowed after cycle 1.

May dose modify/hold either ibrutinib, copanlisib or both as clinically indicated			
Thrombocytopenia	Grade 1 (PLT < LLN - $75 \times 10^9/L$) Grade 2 (PLT < $75 - 50 \times 10^9/L$)	Maintain ibrutinib dose	Maintain copanlisib dose
	Grade 3 (PLT < $50-25 \times 10^9/L$)	
Delay ibrutinib dose until resolves to \leq Grade 1, then: If resolved \leq 7 days, then maintain dose level If resolved $>$ 7 days, then reduce 1 dose level
	Delay copanlisib infusion until platelet resolves to $>75k$

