	Grade 4 (PLT < 25 x 10 ⁹ /L)	Delay ibrutinib dose until resolves to ≤ Grade 1, then reduce 1 dose level	Dose reduction by 1 dose level lower at the investigator's discretion. If more dose reductions are required than allowed per protocol, discontinue copanlisib permanently. The lowest dose level is 30 mg.
Dose modify/hold ibrutinib because of association with hemorrhagic event. May dose modify/hold copanlisib as clinically indicated			
Bleeding	Grade 1 (mild symptoms; no intervention indicated)	Maintain ibrutinib dose	Maintain copanlisib dose
	Grade 2 bleeding (medical intervention indicated/cauterization)	Omit ibrutinib dose until resolves to ≤ Grade 1, then reduce 1 dose level ibrutinib	Delay copanlisib infusion Dose reduction by 1 dose level lower at the investigator's discretion. If more dose reductions are required than allowed per protocol, discontinue copanlisib permanently. The lowest dose level is 30 mg.
	Grade ≥ 3 hemorrhage or hemorrhage resulting in intraocular bleeding causing loss of vision, transfusion of ≥ 2 units PRBCs, and any intracranial hemorrhage	Discontinue ibrutinib	Discontinue copanlisib
RENAL	May dose modify/hold either ibrutinib, copanlisib or both as clinically indicated		
Creatinine elevation	Grade 1 (Cr < 2 x ULN)	Maintain ibrutinib dose	Maintain copanlisib dose
	Grade 2 (Cr 2-3x ULN)	Delay ibrutinib dose until resolves to ≤ Grade 1, then: If resolved ≤ 7 days, then maintain dose level If resolved > 7 days, then reduce 1 dose level	Maintain copanlisib dose
	Grade ≥ 3 (Cr > 3-6 x ULN)	Discontinue ibrutinib	First occurrence: Delay copanlisib infusion until resolves to ≤ Grade 2, no change to next dose Second and Third occurrence: Delay copanlisib infusion until resolves to ≤ Grade 2, decrease by one dose level Fourth occurrence: Discontinue copanlisib *Any grade 4 occurrence: discontinue copanlisib
PULMONARY	Dose modify/hold copanlisib because of association with pneumonitis. May dose modify/hold ibrutinib as clinically indicated		
Pneumonitis	Grade 1		Dose delay copanlisib while treating infection. Resume at same dose once infection resolves
	Grade 2		Dose delay until resolves to ≤ Grade 1. Decrease by one dose level. Second occurrence: Discontinue therapy If no symptom recovery ≤ Grade 1 within 28 days CT scan with lung windows. Consider pulmonary function testing includes: spirometry, DLCO, and room air O ₂ saturation at rest. Repeat at least every 8 weeks (+/- 1)

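### Table 9-7's anemia rule starts and ends the copanlisib delay at Grade 3, and Table 9-1's hemoglobin limits do not reach Days 8 and 15

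*Combined protocol and SAP*

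**What the plan says.** Three parts of the protocol bear on giving copanlisib to a patient with low hemoglobin.

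- **Section 9.7, Table 9-7, anemia row.** The trigger is Grade 3 or higher, which the row itself equates with Hgb below 8 g/dL. The copanlisib instruction is "Delay copanlisib infusion until Hgb resolves to \leq grade 3". Dose reduction is left to the investigator.
- **Section 9.1.1, Table 9-1.** Hemoglobin must be at least 8 g/dL. The column is headed "Criteria for Day 1 dose (Cycle 2 and higher". Footnote a makes an exception for Hgb from 6 to below 8 g/dL: "it is permissible to give the study drug dose as scheduled and transfuse within 48 hours after the dose". It applies if the patient is hemodynamically stable and the investigator judges that benefit outweighs risk, and the rationale must be recorded.
- **Section 9.7, surrounding text.** For expansion-phase patients, "the dose must be held per these guidelines". After Cycle 1, either drug may be interrupted for up to 28 days "for any reason and then resumed at same or reduced dose". A note to Table 9-7 makes hold and reduction mandatory for a drug with which a toxicity is associated.

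**The concern.** A delay rule works only if its release condition lies outside its trigger range. Here both include Grade 3. Section 9.7 makes Table 9-7 binding in the expansion phase, so this is operative safety text.

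The gap matters mainly on Days 8 and 15, because Table 9-1 is confined to Day 1. The same hemoglobin value would meet a floor and documented exception conditions on Day 1 of Cycle 2 or later, and no required hold one week later. The mandatory hold in the note to Table 9-7 depends on attribution to one drug. Attribution is not automatic: Sections 11.5 and 11.7 list lowered hemoglobin or anemia as likely (above 20%) for both ibrutinib and copanlisib.

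**Working it through.** No arithmetic applies, and the plan gives no figure to reproduce. The check compares trigger and release grades.

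**Anemia row as written**

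- Trigger set: Grades 3 and 4 (Hgb below 8 g/dL).
- Release set: Grade 3 and lower.
- Overlap: Grade 3.
- Grade 3 patient: trigger and release hold together, so the delay has zero length.
- Grade 4 patient: the delay ends on reaching Grade 3, which the row places below 8 g/dL.
- The documents give no Hgb value that separates Grade 3 from Grade 4, so the release condition supplies no numeric floor.

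**The same test on other copanlisib rows of Table 9-7**

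| Row | Trigger | Release | Overlap | Table 9-1, Day 1 |
|---|---|---|---|---|
| Anemia | Grade 3 or higher, Hgb <8 g/dL | Grade 3 or lower | Grade 3 | Hgb ≥8; 6 to <8 under footnote a |
| Neutropenia ("Delay copanlisib infusion until ANC resolves to") | Grade 3 or higher, ANC <1.0 | below Grade 3 | none | ANC ≥1; no exception |
| Thrombocytopenia ("Delay copanlisib infusion until platelet resolves to") | Grade 3, platelets <50 | above 75k | none | ≥75; 50 to <75 if disease-related, footnote b |
| Creatinine ("First occurrence: Delay copanlisib infusion until resolves to") | Grade 3 or higher | Grade 2 or lower | none | not listed |

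Of these four rows, only anemia has a release that overlaps its trigger.

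**Which rule applies on which day**

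- Day 1, Cycle 2 and later: Table 9-1 requires Hgb of at least 8 g/dL, or footnote a's conditions from 6 to below 8 g/dL. The faulty row does little harm here.
- Days 8 and 15: Table 9-1 does not apply. The Table 9-7 row is the only specific hemoglobin rule, and it requires no hold at Grade 3.

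**The row with release below Grade 3**

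The release set becomes Grade 2 and lower, that is, Hgb of at least 8 g/dL by the row's own cut. The overlap disappears, and the delay applies at Grades 3 and 4. That change alone would, however, require a delay on Day 1 for a patient whom footnote a allows to be dosed on schedule, so the exception has to be written into the row.

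**The case against.** The strongest reply is that the symbol may be deliberate. Footnote a openly allows dosing at 6 to below 8 g/dL, and a release at Grade 3 is compatible with that. Table 9-1 gives ANC no exception and the neutropenia row releases below Grade 3; it gives hemoglobin an exception and the anemia row releases at Grade 3. The platelet row breaks the pattern: footnote b allows 50 to below 75 if disease-related, yet Table 9-7 releases only above 75k. Intent is therefore unproven either way. A reader might infer a plain misprint, but the documents do not establish one. The text read from the PDF does show different symbols in the anemia and neutropenia rows, so a reading error cannot be presumed, though the source page should be checked.

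The deliberate reading does not rescue the row. It carries neither the 6 g/dL floor nor footnote a's conditions, and had a hold at Grade 4 only been meant, the trigger would have said so.

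A second reply is that other safeguards exist. The row still tells the investigator to delay below 8 g/dL, interruption is allowed at discretion, Section 9.7 holds the dose when treatment criteria are not met, and the note to Table 9-7 compels a hold after attribution. These narrow the gap without closing it. Discretion is not a requirement, the general hold needs a criterion that fails, and on Days 8 and 15 the specific hemoglobin criterion is this row.

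**Conclusion.** The point stands in a limited form. As written, the anemia row does not work as a delay rule: it has no effect at Grade 3, and it releases Grade 4 patients below 8 g/dL. The practical gap is on Days 8 and 15, where Grade 3 anemia meets no mandatory hold, floor or exception conditions unless it is associated with one drug.

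A reader might infer that anemic patients may be dosed without restriction, or that a number wrongly dosed can be estimated. The documents support neither.

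- Day 1 of Cycle 2 and later is gated, and investigators may hold on any day.
- No anemia rate is given for the combination. The 0 to 9% Grade 3 or 4 range in Section 11.6 is for ibrutinib, while copanlisib lists anemia as likely in its own right.
- The number of infusions varies. Section 4.3 holds copanlisib after a complete response, but other patients may continue for up to 36 cycles.

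The number of patients or infusions affected therefore cannot be derived. No sample size, error rate, stopping boundary or analysis changes. The conclusion assumes that the symbol on the source page matches the text read from the PDF. This is a safety-wording correction that should be made.

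**What to change.** First confirm the symbol on the source page. Then amend the anemia row of Table 9-7 so that copanlisib is delayed until anemia is below Grade 3 (Hgb of at least 8 g/dL), with one exception: dosing at Hgb 6 to below 8 g/dL only under all of Table 9-1 footnote a's conditions (hemodynamic stability, benefit judged to outweigh risk, transfusion within 48 hours after the dose, and recorded rationale). State that the rule covers infusions on Days 1, 8 and 15. Writing the exception into the row keeps it consistent with footnote a, and tying release to hemoglobin values removes the need for a Grade 3/4 boundary that the protocol does not give.

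The cost is one corrected symbol and one cross-reference, by amendment, and some additional delayed infusions. Sample size, endpoints and analysis are untouched.

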			week), (or as per local practice) until return to within normal limits. Consider a bronchoscopy with biopsy and / or BAL.
	Grade \geq 3		Discontinue copanlisib
GASTROINTESTINAL	May dose modify/hold either ibrutinib, copanlisib or both as clinically indicated		
(*for patients with Gilbert Syndrome these dose modifications apply to changes in direct bilirubin only, Bilirubin will be fractionated if elevated)	Grade 1 ($>$ ULN - 1.5 \times ULN)	Maintain ibrutinib dose per investigator discretion	Maintain copanlisib dose level with LFTs* monitored as per protocol
	Grade 2 ($>$ 1.5 - 3.0 \times ULN) with ALT or AST \leq 3.0 \times ULN	Dose adjustments of ibrutinib per investigator discretion	Omit dose until resolves to \leq Grade 1, then: If resolved \leq 7 days, then maintain dose level If resolved $>$ 7 days, then reduce 1 dose level
	Grade 3 ($>$ 3.0 - 10.0 \times ULN) with ALT or AST \leq 3.0 \times ULN		Omit dose until resolves to \leq Grade 1, then: If resolved \leq 7 days, then maintain dose level If resolved $>$ 7 days, then discontinue
	Grade 4 ($>$ 10.0 \times ULN)	Discontinue ibrutinib	Discontinue copanlisib
Note: confounding factors and/or alternative causes for increased transaminases like concomitant medications, infection, hepato-biliary disorder, obstruction, liver metastasis, etc. should be excluded before dose interruption/reduction	Grade 1 ($>$ ULN - 3.0 \times ULN)	Maintain ibrutinib dose per investigator discretion	Maintain dose level with LFTs monitored as per protocol
	Grade 2 ($>$ 3.0 - 5.0 \times ULN) without total bilirubin elevation to $>$ 2.0 \times ULN	Dose adjustments of ibrutinib per investigator discretion	Maintain dose or reduce 1 dose level of copanlisib.
	Grade 3 ($>$ 5.0 - 20.0 \times ULN) without total bilirubin elevation to $>$ 2.0 \times ULN		Omit dose until resolves to \leq Grade 1, then reduce 1 dose level. If no recovery in \leq 28 days discontinue copanlisib, patient off study
	Grade 4 ($>$ 20.0 \times ULN) without bilirubin elevation to $>$ 2.0 \times ULN	Discontinue ibrutinib	Discontinue copanlisib

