Upon initiation of ibrutinib, a temporary increase in lymphocyte counts (i.e., $\geq 50\%$ increase from baseline and above absolute lymphocyte count of 5,000/MCL) occurred in 33% of patients in the MCL study. The onset of isolated lymphocytosis occurs during the first few weeks of ibrutinib therapy and resolves by a median of 8 weeks. High number of circulating malignant cells ($>400,000/\text{mCL}$) may confer increased risk; these patients should be closely monitored. Patients with MCL who develop lymphocytosis greater than 400,000/mCL have developed intracranial hemorrhage, lethargy, gait instability, and headache. However, some of these cases were in the setting of disease progression. Administer supportive care such as hydration and/or leukapheresis as indicated. This observed transient lymphocytosis is usually not associated with an adverse event and should not be considered progressive disease in the absence of other clinical findings.

Management of hematologic toxicity associated with copanlisib

Neutropenia and febrile neutropenia are listed in the current version of investigator's brochure for copanlisib as expected adverse events. Please refer to Table 9-7 for dose modifications based on hematologic toxicity. If the guidelines are not followed, the rationale for other measures is to be documented in detail in the patient's medical record.

Management of Pneumonitis in patients receiving copanlisib

Non-infectious pneumonitis has been associated with PI3K inhibitors. The investigator is requested to differentiate between non-infectious pneumonitis, and infectious pneumonitis (viral, bacterial, fungal), aspiration pneumonitis, or other pneumonitis clearly not due to a potential hypersensitivity reaction to the copanlisib infusion; and provide the basis for his/her assessment that it is infectious or other, as appropriate. The investigator is requested to report with the most specific clinical terms to describe the condition, not simple “pneumonitis”.

In the event of suspected non-infectious pneumonitis, modify copanlisib treatment as per guidelines in Table 9-7 and Table 9-8. If the guidelines are not followed, the rationale for other measures is to be documented in detail in the patient’s medical record.

Table 9-8. Management of Pneumonitis				
Worst Grade	Recommended Investigations	Recommended Management	Action with Copanlisib	Retreatment Dose after Recovery

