Grade 1	CT scans with lung windows. Repeat at least every 8 weeks (+/- 1 week), (or as per local practice) until return to within normal limits.	No specific therapy is required	No change	NA
Grade 2	CT scan with lung windows. Consider pulmonary function testing includes: spirometry, DLCO, and room air O ₂ saturation at rest. Repeat at least every 8 weeks (+/- 1 week), (or as per local practice) until return to within normal limits. Consider a bronchoscopy with biopsy and / or BAL.	Symptomatic only. Consider corticosteroids if symptoms are troublesome.	Dose interruption until recovery to ≤ grade 1	Decrease dose to the next lowest dose level, minimum dose is 30mg copanlisib ^a
Grade 3	CT scan with lung windows and pulmonary function testing includes: spirometry, DLCO, and room air O ₂ saturation at rest. Repeat at least every 8 weeks (+/- 1 week), (or as per local practice) until return to within normal limits. Bronchoscopy with biopsy and / or BAL is recommended.	Consider corticosteroids if infective origin is ruled out. Taper as medically indicated.	Discontinue copanlisib	NA
Grade 4	CT scan with lung windows and required pulmonary function testing, if possible, includes: spirometry, DLCO, and room air O ₂ saturation at rest. Repeat at least every 8 weeks (+/- 1 week), (or as per local practice) until return to within normal limits. Bronchoscopy with biopsy and / or BAL is recommended if possible.	Consider corticosteroids if infective origin is ruled out. Taper as medically indicated.	Discontinue copanlisib	NA

Guidelines for the treatment of copanlisib induced arterial hypertension

No dose should be given if blood pressure is ≥ 150/90 mmHg. Antihypertensive medication may be given to control the increased blood pressure. Dosing can proceed on the scheduled day if there are at least 2 consecutive measurements <150/90 mmHg. Otherwise dosing must be delayed.

If drug-related arterial hypertension (post-dose blood pressure of CTCAE Grade 3 or \geq 160/100 mmHg) is not manageable with optimal antihypertensive treatment, the dose for the subsequent copanlisib administrations may be reduced by 1 or 2 dose levels at the investigator's discretion. Patients with a post-dose blood pressure that may have life-threatening consequences (e.g. malignant arterial hypertension, transient or permanent neurologic deficit, hypertensive crisis) must permanently discontinue the study drug. Please see table 9-7.

Treatment of blood pressure increases associated with copanlisib

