13.0 CRITERIA FOR REMOVAL FROM STUDY

Patients may voluntarily withdraw from the study or be removed from the study at the discretion of the investigator at any time. Patients may be withdrawn from the study if any of the following occur:

- Disease progression. However, if progression develops after CR while patient is on ibrutinib alone, patients could restart treatment upon radiographic and pathologic expression of disease.
- Ineligibility (at the pretreatment evaluation) of the patient as defined in the inclusion/ exclusion criteria
- Treatment will be discontinued at the request of the patient, refusal of therapy, non-compliance, or upon the development of an intercurrent significant medical illness.
- Significant protocol violation
- Unacceptable toxicity
 - Grade 4 arterial hypertension
 - Grade 4 dermatologic toxicity
 - Non-infectious pneumonitis
 - Drug induced clinically relevant pancreatitis
 - Grade ≥ 3 hypersensitivity reaction
- Decision by the investigator that termination is in the patient's best medical interest.
- Loss to follow-up

- Development of active HBV or HCV infection, hepatitis, or HIV infection
- Pregnancy or a positive pregnancy test
- Death of the patient

In addition to the general study treatment withdrawal criteria, the following study specific criteria will also require premature study treatment discontinuation:

- Use of prohibited medication
- Start of any other anti-neoplastic therapy

If a study treatment withdrawal occurs, or if the patient fails to return for visits, the investigator must determine the primary reason for a patient's premature withdrawal from study treatment and record this information on the End of Treatment CRF page.

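### Grade 1-2 pneumonitis has conflicting instructions across Table 9-7, Table 9-8 and Section 13

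*Combined protocol and SAP*

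**What the plan says.** Four places in the combined protocol and SAP govern pneumonitis.

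- **Section 9.7, Table 9-7, pulmonary rows.** The copanlisib cell for the mildest grade reads "Dose delay copanlisib while treating infection. Resume at same dose once infection resolves". One row down, for a Grade 2 event, the cell instead reads "Dose delay until resolves to ≤ Grade 1. Decrease by one dose level. Second occurrence: Discontinue therapy". From Grade 3 upwards the action is "Discontinue copanlisib".
- **Section 9.8, Table 9-8.** Grade 1: "No specific therapy is required", with copanlisib unchanged. Grade 2: "Dose interruption until recovery to ≤ grade 1", then retreatment at the next lower level. Grades 3 and 4: copanlisib is discontinued.
- **Section 9.8, text before Table 9-8.** For suspected non-infectious pneumonitis the investigator is to "modify copanlisib treatment as per guidelines in Table 9-7 and Table 9-8", and must document the rationale for any departure.
- **Section 13.** Under unacceptable toxicity the list includes "Non-infectious pneumonitis", without a grade. The lead-in to the list is permissive.

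Sections 10.2 and 10.3 continue treatment until, among other things, unacceptable toxicity or the discontinuation criteria are met; Section 10.3 refers to Section 13 for this.

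**The concern.** An investigator facing a Grade 1 non-infectious event can find text that points to holding copanlisib, to continuing it unchanged, or to ending study treatment. At Grade 2 the choice is between retreatment at a lower level and removal. Two patients with the same event could therefore be managed differently depending on the page consulted, which is first a patient-safety matter.

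It also reaches the analysis in two ways. Section 9.2 counts an adverse event that delays dosing by more than 7 consecutive days in cycle 1 as a DLT, and two DLTs at a dose level stop escalation. Section 14.2 counts treatment discontinuation for an adverse event as an EFS event. Both counts would then depend partly on which instruction was followed.

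**Working it through.** **Step 1. Set the instructions side by side (non-infectious event, action on copanlisib).**

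| Grade | Table 9-7 | Table 9-8 | Section 13 | Consistent? |
|---|---|---|---|---|
| 1 | Hold; resume at same dose (worded around infection) | Unchanged | Listed, no grade | No |
| 2, first event | Hold to Grade 1 or better; one level down | Hold to Grade 1 or better; next lower level | Listed, no grade | Tables agree; Section 13 differs |
| 2, recurrence after reduction | Discontinue | No entry, but see step 2 | Listed, no grade | Yes |
| 3 or above | Discontinue | Discontinue | Listed, no grade | Yes |

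**Step 2. Recurrence.** Table 9-8 has no entry for a second Grade 2 event. Section 9.7 has a general rule: if the same toxicity returns at the same or worse severity after resumption at a lower dose, therapy must stop. Table 9-8 resumes Grade 2 patients at a lower level, so a Grade 2 recurrence leads to discontinuation under either table.

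**Step 3. Force of Section 13.**
- The lead-in says only that patients may be withdrawn.
- Against that, Sections 10.2 and 10.3 end treatment at unacceptable toxicity or when discontinuation criteria are met.
- Section 13 then introduces further criteria as ones that will also require discontinuation, which treats the preceding list as binding.
- On grade, the neighbouring bullets for hypertension (Grade 4), dermatologic toxicity (Grade 4) and hypersensitivity (Grade 3 or above) state one, and the pancreatitis bullet is limited to clinically relevant cases. The pneumonitis bullet has no limit of either kind.

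**Step 4. Does the conflict touch the stopping rule?** The Section 14.2 rule pools treatment-related Grade 3 or higher pneumonitis and colitis. I read the boundary b(n) as 1 event for patient 1, 2 for patients 2-14, 3 for patients 15-33 and 4 for patients 34-45. With f(n,k) the probability of k events after n patients without having stopped,

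f(n,k) = f(n-1,k)(1-p) + f(n-1,k-1)p for k < b(n),

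and the stopping probability is the total mass that reaches b(n).

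| True rate p | 0.025 | 0.04 | 0.055 | 0.07 | 0.085 | 0.10 |
|---|---|---|---|---|---|---|
| Stated | 0.092 | 0.224 | 0.377 | 0.528 | 0.661 | 0.767 |
| Recomputed | 0.097 | 0.224 | 0.377 | 0.528 | 0.661 | 0.767 |

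Five of six values agree to three decimals; the first differs by 0.005. The inputs are the boundary, the 45 patients and the Grade 3 or higher rate. No Grade 1-2 instruction enters, so reconciling those instructions changes none of these figures.

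**Step 5. How often might it arise?** Section 11.7 places pneumonitis among copanlisib effects seen in 4-20% of patients. Assuming that range applies to this combination and to the 45 patients: 0.04 × 45 = 1.8 and 0.20 × 45 = 9, so about 2 to 9 patients. That section does not break the range down by grade, so the Grade 1-2 number may be smaller.

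**Step 6. Endpoint routes.**
- *DLT:* a Table 9-7 hold lasting more than 7 consecutive days in cycle 1 could meet the criterion; a Table 9-8 Grade 1 patient, with dosing unchanged, would not meet it by that route. This is conditional. Section 9.7 introduces the Table 9-7 steps for expansion-phase patients, and the DLT criterion itself cites Table 9-6, although the Section 9.8 referral to Table 9-7 is not limited by phase.
- *EFS:* ending treatment for the event is an EFS event; a hold or no change is not.

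**The case against.** The strongest reply at Grade 1 is that the Table 9-7 cell speaks of treating an infection, while Table 9-8 is introduced for suspected non-infectious pneumonitis. With no infection to treat, the Table 9-7 cell has nothing to act on and Table 9-8 can simply be followed. This is plausible as intent, and it is why the two cells should not be called strictly impossible to obey together. But the row is labelled pneumonitis, sits under a heading about copanlisib's association with it, and Section 9.8 routes non-infectious events to it. If infection was meant, Table 9-7 has no Grade 1 instruction for the event Section 9.8 sends there.

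The second reply is that a permissive Section 13 does not contradict tables that allow retreatment. That is fair as far as the lead-in goes. Sections 10.2 and 10.3 and the later wording of Section 13 leave the force of the list unclear, so what remains is a real ambiguity and not a flat third command.

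A reader might also infer stronger points that the documents do not support:

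- That the conflict alters the stopping-rule count. The rule counts only Grade 3 or higher events, where both tables agree. Any link would run through later worsening of milder events, which the documents give no means to size.
- That only Table 9-7 limits a second Grade 2 event. The general recurrence rule in Section 9.7 covers it.
- That each patient handled differently moves EFS by 1/33 = 3.0 percentage points. EFS is a Kaplan-Meier estimate covering both phases, so the effect depends on timing, censoring and the analysis set.
- That the nine earlier cases in Section 11.8 size the problem. They are reported without grade or a pneumonitis-specific denominator.

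**Conclusion.** The inconsistency is real and confined to Grades 1-2. At Grade 1 the two tables differ and it is unclear whether the Table 9-7 cell is for infectious events only. At Grades 1-2 both tables permit copanlisib to continue or resume while Section 13 lists the event, ungraded, as unacceptable toxicity with unclear force. At Grade 3 and above there is no conflict.

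No numerical effect on an endpoint can be derived. On the assumption in step 5, a handful of patients (about 2 to 9 of 45, any grade) could have pneumonitis. For those with Grade 1-2 events, the text followed can change safety management and the EFS count and, if Table 9-7 is applied in phase I cycle 1, the DLT count. The response-based primary endpoint of phase II and the stopping-rule operating characteristics do not rest on this point. The conclusion rests on the text alone and should be corrected, chiefly for safety and for consistent event counting.

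**What to change.** The sponsor should reconcile the pneumonitis rows of Table 9-7, Table 9-8 and the Section 13 bullet so that:

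1. each grade has one instruction, or one table refers to the other;
2. each entry states whether it applies to infectious or non-infectious events;
3. Section 13 states whether its list is mandatory or permissive, in line with Sections 10.2 and 10.3, and at what grade the pneumonitis bullet applies.

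Which clinical rule is right is for the sponsor to decide; none is proposed here. The cost is a protocol wording amendment, with no added visits, tests or patients and no change to the sample size or stopping boundaries.
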